### Lactate dynamics and exercise

In humans, there is a linear relationship between systemic lactate concentration and brain lactate uptake at physiological concentrations and lactate can contribute to as much as 60% of cerebral metabolism when transporters are saturated. [40] The kinetics of lactate entry into brain indicate the blood brain barrier is about half as permeable to lactate as glucose, but that intracellular uptake of lactate is greater. [49] Recent evidence suggests that the FDG signal is driven by glial glucose use, [50] and that increased supply of peripheral lactate may reduce the FDG-PET signal. [51, 52] Regardless of source, increased lactate supply should drop the FDG signal due to increased availability to both cell types.

**Fig 1. Schematic figure for the effect of exercise on brain glucose metabolism.** (A) It has been proposed that glycolysis within glia is a key source for neuronal energy at rest, likely via the intermediate metabolite lactate. B) Acute exercise increases circulating lactate levels, which can permeate the blood brain barrier and freely enter the brain. Lactate can be directly taken up into both neurons and glia, which would spare glucose and decrease the FDG signal.

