#### **Acute vs. Chronic effects of exercise on brain glucose metabolism**

The directionality of change in brain glucose metabolism following acute exercise likely will not reflect the directionality of change in brain glucose metabolism following chronic exercise. While we expect to observe a decrease in glucose uptake following acute exercise due in part to the availability of lactate for oxidation, it has been shown that a 12wk exercise *intervention* is associated with an increase in brain glucose metabolism post-intervention. [56] Likewise, inactive individuals show reduced FDG signal with age, while active individuals do not, suggesting lifestyle attenuates the age-related drop in brain glucose metabolism. [70] Interestingly, pre-clinical studies have shown that acute exercise modulates a region-specific upregulation of monocarboxylate (lactate/pyruvate/ketone) and glucose transporters that remain elevated at least 18-24 hrs post-exercise [71]. Other work that examined immunostaining patterns of the glucose transporter isoform 1 (GLUT1) showed upregulation in motor cortex following exercise. [72] Although the effect on other transporter isoforms is unclear, this suggests that plasticity in GLUT1 expression may be related to neuronal activity. Over time, acute exercise-related effects may elicit changes in metabolic transporter expression and localization, and thus predict longer-term outcomes. For example, larger acute drops in brain glucose metabolism due to strenuous exercise may elicit greater/longer term change in expression of transporters and increased resting glucose metabolism, although this remains to be

tested. These ideas are outside of the scope of the current proposal, but the current work will lay the foundation for future investigations and trials to explore such mechanisms.

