## II. Research Plan and Design

Study Objectives:

**Aim 1. Compare the effects of acute, moderate intensity and acute, higher intensity exercise on cerebral glucose metabolism in nondemented (ND) elderly and AD subjects.** ND (n=30) and AD (n=30) subjects will undergo a single bout of moderate intensity (45-55% HRR) or higher intensity (65-75% HRR) exercise to assess the effect of exercise intensity on acute change in brain glucose metabolism (rest to exercise). *We hypothesize that both moderate and high intensity exercise will elicit a drop in global brain glucose metabolism compared to quiet rest, but that the effect will be greater with higher intensity vs. moderate intensity exercise, and greater in ND subjects than in AD subjects.*

**Aim 2. Characterize the effect of both exercise intensities on acute biomarker response and cognition (memory and executive function) in ND and AD subjects.** The acute biomarker response to exercise and the effect on cognition has not been examined in aged or AD cohorts. *We hypothesize that acute higher intensity exercise will elicit a greater blood lactate response (lactate area under the curve; AUC) compared to acute moderate intensity exercise, and that this response will be greater in ND than in AD subjects. We further hypothesize that lactate AUC will track negatively with change in cerebral glucose metabolism and cognitive performance.* Although we will focus on lactate, we will also quantify additional exercise-related biomarkers.

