**FDG-PET imaging:** FDG PET images will be obtained at a satellite location of the University of Kansas Hospital, the KU Cancer Center – Overland Park (KUCC-OP). The scanner is accredited by the American College of Radiology (ACR), and our physicists perform annual required testing by scanning an Esser PET phantom with 18F to assess SUV range, contrast resolution, spatial resolution, and uniformity. In addition to the ACR annual testing, the nuclear medicine department routinely performs quality control procedures on a daily, weekly, and quarterly basis. Frames are reconstructed to a single PET image in native space. Adverse events will be continuously monitored during the imaging session. The radiation dose from the two FDG PET scans will not exceed 2100 mrem. While this exceeds the amount obtained through normal background exposure, it is considered by Radiation Safety to be well below the risk levels acceptable in research and medical practice. PET images will be analyzed using custom software written for Statistical Parametric Mapping (SPM12). Pre- and post-intervention P images will be co-registered. A priori regions of interest masks from the Automated Anatomic Labeling series will be inverse warped to match native space images. The PET images will be standardized to the uptake value of the cerebellum and standardized uptake value ratios (SUVR) will be calculated from native-space ROIs as determined by MRI. Regional SUVR will be compared using paired t-tests or linear mixed models as appropriate.

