### **V. Data Analysis and Reporting**

#### **A. Statistical and Data Analysis:**

The primary statistical analyses for Aims 1-2 utilize paired, pre-, post- acute exercise measurements. As such, we will analyze the data using the two-sample, paired t-tests. This will contrast overall changes in

brain metabolism following acute exercise (i.e., pre- vs. post-exercise differences) and between the intensity groups (moderate vs. higher intensity). We will conduct residual analyses to assess the appropriateness of this methodology to evaluate assumptions of common variance, normally distributed errors, etc. In the event any of the measures do not conform to these foundational assumptions, the nonparametric analogs will be used instead, such as the Wilcoxon rank sum test of the within-subject pre- vs. post-exercise measures. These measures will follow the intent-to-treat principals. Though a randomized design, we will also construct exploratory analyses that incorporate other adjustments using ordinary least squares (OLS) regression on the change scores as the outcomes, also with residual analysis and modified approach if indicated. This will allow for model adjustment to further examine these relationships. One further relationship will involve combining the results of the AD and ND subjects in a single model as described in our Aims. We will use OLS in this context to test for interactions between AD and ND subjects with respect to the acute exercise response (moderate vs. higher intensity) for these pre-/post-exercise change score outcomes. Finally, we will model change score outcomes as functions of the various other change score measures. This approach will enable us to observe how changes in cerebral glucose metabolism are driven by acute-exercise influenced changes in circulating biomarkers. We will conduct similar residual analyses appropriate to the regression models utilized to ensure appropriate inferences are drawn. While descriptive and exploratory in nature, we anticipate that this approach will illuminate and/or confirm our pre-conceived metabolic processes that are related to the acute exercise response, and that it will help identify likely reasons for prior exercise trial successes and failures through mechanistic discovery. We believe this study fits perfectly within the study paradigm for PAR-18-877 by the NIA, which states that identifying precise cellular mechanisms will provide important therapeutic targets.

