Sample size justification. We powered our study based upon our primary variable of interest, cerebral glucose metabolism. Based on previous literature [6], the cerebral metabolic rate of glucose following acute exercise at (70% VO2max) ( $3.18 \pm 0.68$ ) was significantly lower compared with that of resting controls ( $4.25 \pm 0.27$ ). This study produced an effect size of 2.07 based on the independent t test design. However, given the small sample size of that initial study, we conservatively use much lower effect sizes. A two sample paired t test design with an effect size of 1.25 and a sample size of 15 AD subjects allocated to high intensity and 15 AD subjects allocated to moderate exercise would yield an estimated power of 91% using a conservative estimated effect size of 1.25. Dropping down to less than half the effect size produced in the preliminary data to 1.00 still provides 75% power, and using a still conservative 1.50 for the effect size indicates >95% power. (Power calculations were produced by nQuery Advisor® 7.0, 1995-2007.) We plan to recruit the same number of elderly healthy patients in the study. Accounting for a possible 10% attrition rate over the course of the study visits, we propose a total sample size of 60 (30 subjects in each diagnosis group with 15 individuals assigned to moderate and higher intensity acute exercise) Thus, we anticipate recruiting the sample size of 66, which will provide over 90% power based on a conservative estimate of the effect size from the literature and the use of paired difference scores for the primary endpoint, which should reduce variation in the response.

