### **B. Primary Outcome:**

We expect that the global FDG-PET signal will decline following a single bout of acute exercise in AD and ND subjects, and that the drop will be greater from rest to higher intensity exercise compared to the drop from rest to moderate intensity exercise. We further expect that individuals who have a greater lactate AUC in the exercise compared to resting condition (i.e. greater “lactate response”) will have greater drop in cerebral glucose metabolism. This likely means that they are exercising closer to their lactate threshold – the point where blood lactate concentrations begin to increase exponentially. Thus, we expect to see a negative linear relationship between change in lactate AUC and change in cerebral glucose metabolism, and a positive relationship between change in lactate AUC and change in cognitive performance.

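### Aim 1 and V.B concern a global fall in brain glucose metabolism, but no global measure is defined, and the only PET measure described, regional SUVR to the cerebellum, cannot by itself show or exclude one

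*Combined protocol and SAP*

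**What the plan says.** The target is global in two places. Aim 1 (Section II, Research Plan and Design) hypothesises that "both moderate and high intensity exercise will elicit a drop in global brain glucose metabolism compared to quiet rest", with a larger effect at higher intensity. V.B, Primary Outcome, states: "We expect that the global FDG-PET signal will decline following a single bout of acute exercise in AD and ND subjects". Neither place gives a region, a weighting across regions or a unit.

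The primary analysis in V.A contrasts changes in "brain metabolism following acute exercise (i.e., pre- vs. post-exercise differences) and between the intensity groups (moderate vs. higher intensity", and names no PET measure.

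The measurement is described once, under FDG-PET imaging in II.E. Each scan becomes a single image, and then "The PET images will be standardized to the uptake value of the cerebellum and standardized uptake value ratios (SUVR) will be calculated" from atlas regions. The analysis line reads: "Regional SUVR will be compared using paired t-tests or linear mixed models as appropriate". Plain SUV appears in that section only for phantom quality control. No whole-brain value, cerebellar value or absolute metabolic rate is listed as a participant output.

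The sample size paragraph in V.A takes its effect size from a different scale, "the cerebral metabolic rate of glucose following acute exercise".

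**The concern.** A ratio to one part of the brain is being asked to answer a question about the whole brain. If exercise lowers uptake everywhere by the same proportion, which is the plainest reading of a global drop, numerator and denominator fall together and SUVR does not move. Followed as written, the plan could report little or no effect when the hypothesis is true. The comparison of moderate with higher intensity uses the same changes and is exposed in the same way.

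Because cerebellar uptake would not be reported, a reader could not separate the absence of a global drop from a drop that the ratio removed. Leaving the global measure undefined also leaves its choice open until after the data are seen.

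**Working it through.** **1. The plan's own figures.** V.A gives 3.18 (SD 0.68) after exercise and 4.25 (SD 0.27) in resting controls.

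- Pooled SD = sqrt((0.68² + 0.27²)/2) = 0.517.
- Effect size = (4.25 - 3.18)/0.517 = 2.07, as stated.
- Power of a two-sample t-test with 15 per group, two-sided 5% (assumed, since V.A states no alpha): 75.3% at effect size 1.00, 91.0% at 1.25 and 97.7% at 1.50. The plan states 75%, 91% and more than 95%.

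The arithmetic reproduces. The issue is that these figures concern an absolute rate and the planned measure is a ratio.

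**2. Cancellation.** Let uptake be R in a target region and C in the cerebellum, so SUVR = R/C. If the target falls by a fraction f and the cerebellum by c × f, where c is the cerebellar share of the fall, then

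SUVR change = (1 - f)/(1 - c × f) - 1.

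At c = 1 this is zero for any f. Averaging over regions does not help. The mean of R1/C, R2/C and so on equals the mean of the R values divided by C, and a common factor still cancels.

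**3. Size within one arm.** Take f = (4.25 - 3.18)/4.25 = 25.2%. This is a difference between independent groups, borrowed only to give a scale. The share c is not in the documents and is varied as an assumption.

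| Cerebellar share c | Calculation | SUVR change |
|---|---|---|
| 0% | 0.748/1.000 - 1 | -25.2% |
| 50% | 0.748/0.874 - 1 | -14.4% |
| 100% | 0.748/0.748 - 1 | 0% |

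**4. The intensity contrast.** Assume the moderate arm falls half as much (12.6%) and both arms have the same share. The gap is the moderate change minus the higher-intensity change.

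| Share in both arms | Moderate | Higher | Gap (points) |
|---|---|---|---|
| 0% | -12.6% | -25.2% | 12.6 |
| 50% | -6.7% | -14.4% | 7.7 |
| 100% | 0% | 0% | 0 |

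The half-fall assumption is not critical. If the moderate arm falls by 25% of f, the gaps are 18.9, 11.2 and 0. If it falls by 75% of f, they are 6.3, 4.0 and 0. The gap shrinks in each case.

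**5. What plain SUV can and cannot add.** Suppose brain metabolism is unchanged but working muscle takes 10% of the tracer that would have reached the brain (assumed). Whole-brain and cerebellar SUV both fall by 10%, and SUVR changes by 0.9/0.9 - 1 = 0%. A shared metabolic fall of 10% gives the same three numbers. SUV therefore shows what the ratio hides, but does not identify the cause.

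**The case against.** The best defence is that a reference region is a sensible choice in an exercise study. Step 5 shows why: the ratio removes a loss of tracer to muscle that plain SUV would read as a brain effect. That loss may be greater at higher intensity, which would push SUV towards the hypothesised contrast. This stands. It is a merit of the written plan and the reason why SUV should not simply replace SUVR. It does not make SUVR a measure of global change.

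A second defence is that nothing in the documents shows that the cerebellum moves. That is also correct. The background section on lactate says: "Regardless of source, increased lactate supply should drop the FDG signal due to increased availability to both cell types". This concerns neurons and glia, not regions. The section on acute and chronic effects says that "acute exercise modulates a region-specific upregulation of monocarboxylate (lactate/pyruvate/ketone) and glucose transporters", but this is preclinical transporter work and does not mention cerebellar FDG uptake. Neither passage shows that the cerebellum is affected or that it is spared, and no planned output would settle the matter.

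Third, the lack of any mention of injected activity or scan-day weight is weak evidence that they are not recorded. II.A commits to strict timing of tracer injection and scanning, and the available text of the visit descriptions there breaks off mid-sentence. The records should be confirmed, not presumed absent.

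**Conclusion.** The point holds as a gap between the stated outcome and the described measure. The hypothesis and primary outcome are global, no global measure is defined, and cerebellum-referenced SUVR gives only change relative to the cerebellum. The cancellation is algebra and needs no assumption. Its size in this trial is unknown: between none and all of the effect for shares of 0 to 100%, which is -25.2% to 0% on the illustrative fall.

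Three stronger readings are tempting and are not supported:

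- A reader might infer that the trial will miss a true drop. That needs a cerebellar fall, and the documents are silent on it.
- A reader might infer that the intensity contrast could widen or reverse. That can require different cerebellar shares in the two randomised arms, and nothing in the documents suggests such a difference.
- A reader might convert the cancellation into a loss of power. No power on the SUVR scale can be derived, because the documents give neither a cerebellar share nor an SD for SUVR change.

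Regional SUVR change remains interpretable as relative change. This is a definition and reporting correction to the primary outcome that should be made before analysis. It is not a flaw that invalidates the design.

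**What to change.** 1. In V.B, define the global outcome: the region, whether it includes the cerebellum, the weighting across regions and the unit. State which measure is primary.
2. From the images already planned, compute whole-brain and cerebellar SUV at rest and at exercise. First confirm that injected activity, injection time and body weight are on record for each scan. Report both SUV changes beside the SUVR change, with 95% confidence intervals by intensity and diagnosis.
3. State in advance that SUVR supports only change relative to the cerebellum, and that a null SUVR result will not be reported as absence of a global drop. Interpret the measures jointly from their estimates and intervals, not by which one reaches significance.
4. In the sample size section, state that the effect size comes from an absolute metabolic rate and has not been verified for SUVR.

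The cost is wording plus a small extra computation per scan, with no added scan, visit or blood draw. If the records turn out to be incomplete, items 1, 3 and 4 can still be done. The limitation should be written down too: SUV is open to tracer uptake by working muscle, SUVR is blind to shared change, and neither alone is a validated global endpoint.

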**Resting Protocol (Visit 2 or 3 – counterbalanced between subjects)**

Participants will arrive for FDG PET after having fasted for a minimum of 8 hours and will have a catheter placed for IV administration of FDG. Draw 1 will be performed right before FDG bolus is administered. Subjects will begin resting and will receive a single IV bolus of FDG minutes into resting. Draw 2 will be taken after 5 minutes of rest. Draw 3 will be taken after 20 minutes of rest. The participant will be moved to the PET scanner at minute 25 and Draw 4 will be taken at 30 minutes. The scan will start immediately at minute 35. After the scan is complete a blood draw will be taken at minute 45 and a short cognitive performance test (NIH Toolbox Cognition Battery) will be performed. The final blood draw will be taken after the testing is complete, at approximately minute 75.

**Acute Exercise Protocol (Visit 2 or 3 – counterbalanced between subjects):** Participants will report to the scan room for the baseline blood draw. After mounting the bicycle, subjects will be asked to begin exercise (warm-up) 5 min before the injection of FDG. One minute prior to warm up, while the subject is resting and sitting on the bicycle, Draw 1 will be taken. At time T0 the subject will pedal at 60-70 revolutions per minute at an equivalent of 40W for 2 minutes. The study coordinator will oversee the workload and provide instruction to the participant as needed. Over the next 3 minutes, the study coordinator will increase the workload to either 45-55% or 65-75% of HRR (depending on randomization group). Blood pressure will be

monitored during the warm up. Four minutes after the warmup begins (1 min prior to FDG injection), Draw 2 will be taken. Immediately following the 5 min warm up, FDG will be injected through the IV catheter that was placed prior to exercise. Following injection, participants will maintain cycling at either 45-55% or 65-75% of their HRR for 15 min. We will use an electronically-braked cycle ergometer (Lode, Groningen, Netherlands) to precisely control HR and workload. Rating of perceived exertion (RPE) will be collected every 2 minutes to assess effort. Participants will maintain a consistent pedaling rate (60-70 rpm) as this may affect physiological variables. [111] Immediately following the 15 min exercise at the target intensity, Draw 3 will be taken. At this time, the participant will begin a cool down period that lasts 5 min. Blood pressure will be monitored during the cooldown. The participant will dismount the bicycle and move to the scanner table. Draw 4 will be taken at 30 minutes before the scan. After the scan is complete a blood draw will be taken at minute 45 and a short cognitive performance test (NIH Toolbox Cognition Battery) will be performed. The final blood draw will be taken after the scan is complete, at minute 75. We will provide up to 120mL of water as needed to account for any dehydration that may affect blood volume during exercise. The amount of water consumed by each participant during exercise will be noted by the study coordinator.

Cognitive performance analyses (Visits 2 and 3): Most work assessing acute cognitive change following exercise has focused on executive function testing. We will administer a short battery of cognitive tests using the NIH Toolbox Cognition Battery on an iPad 5 minutes following the end of the FDG-PET scan at minute 50. These will assess executive function, attention, processing speed and episodic memory, given data linking these domains with exercise and physical activity.[1, 112] Different versions of these tests will be used between the resting and exercise visits where available.

MRI Scan (Visit 4): Structural MRI will use a Siemens 3.0 Tesla Skyra MRI scanner. We will obtain high resolution T1 weighted (MPRAGE) images following the ADNI2 standard. High-res T1 weighted anatomic images provide gross anatomy with high gray-white matter contrast (MP-RAGE; 1x1x1mm voxels; TR=2300, TE=2.98, TI=900, FOV, 1mm thickness, flip angle 9°). Neuroimages will be processed via Freesurfer. [81]

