### A. Study Type and Design:

This is a cross-sectional, observational study to determine the effect of acute exercise on cerebral glucose metabolism in cognitively healthy elderly (n=30) and Probable AD (n=30). There will be 4 study visits. Individuals will be recruited from the KU Alzheimer's Disease Center (KU ADC) Clinical Cohort and Eligibility Database. The study visits are explained below, and a timeline for the FDG-PET scan visits is given in Figure 2.

Figure 2A. Resting Visit Timeline

[figure not shown]
[figure not shown]

Figure 2B. Exercise Visit Timeline

uptake, the subject will sit quietly. Background factors (lighting, noise, etc.) will be identical between V2 and V3, with the only difference being the acute exercise bout (Fig 2, A-B). We will adhere to strict timing regarding blood draws, tracer injection, and scan time. Following the scan, a short battery of executive function tests (see detailed methods) will be administered (Table 2). \*V2 and V3 will be counterbalanced.

**Visit 2/3 (~90 mins):** V3 will consist of an FDG-PET scan in early morning, after an overnight (8hr) fast, following exercise. The timing for blood draws and PET scan will match V2. *For both visits we will inject the radiotracer at the timepoint that corresponds to completion of the 5 min warm-up.* In pilot work, we showed that blood lactate levels are elevated at this time using this exact exercise protocol (Fig 3). Following the scan, a short battery of executive function tests (see detailed methods) will be administered. \*V2 and V3 will be counterbalanced.

**Visit 4. (~30 mins):** We will obtain a structural MRI, which will enhance the analysis of the PET images.

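### The plan does not say how alternate cognitive test versions are assigned, so a version locked to rest or to exercise, which would confound Aim 2's rest-to-exercise cognitive change, is not ruled out

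*Combined protocol and SAP*

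**What the plan says.** Section II.E, under Cognitive performance analyses (Visits 2 and 3), has a short NIH Toolbox battery given after each PET scan, once on the resting day and once on the exercise day. On alternate forms it says only: "Different versions of these tests will be used between the resting and exercise visits where available".

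The order of the two days is controlled. Section II.A states that "V2 and V3 will be counterbalanced", and the Resting and Acute Exercise Protocol headings in II.E describe each condition as falling on Visit 2 or 3, "counterbalanced between subjects". Neither place mentions test version, and neither says that order is balanced within diagnosis or intensity group.

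Cognition belongs to Aim 2: "Characterize the effect of both exercise intensities on acute biomarker response and cognition (memory and executive function) in ND and AD subjects". For the analysis, section V.A says: "The primary statistical analyses for Aims 1-2 utilize paired, pre-, post- acute exercise measurements". It adds exploratory least-squares models on change scores, with no covariate for version or visit order. Section V.B also expects "a positive relationship between change in lactate AUC and change in cognitive performance". No equivalence of versions or equated scoring is described.

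**The concern.** Using two versions is sensible, because it limits recall of items from the first session. It also brings in a second factor that differs between a participant's two sessions. The plan needs a rule that keeps this factor from following the condition, and it has none. The one sentence on the subject describes the two sessions by condition, so a coordinator could reasonably keep one form for resting days and the other for exercise days and still comply.

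Each participant's cognitive change would then be the exercise effect plus the difference in difficulty. Counterbalancing visit order would not help, because the form would move with the condition. Once the data were collected, no model could separate the two, because no participant would have taken the other form under either condition. The study otherwise takes care to keep the two PET days alike apart from the exercise bout, and this gap sits badly with that intention.

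**Working it through.** **1. The plan's own figure.** The documents give no figure for cognition or for version difficulty. The only power figure is for cerebral glucose metabolism: "A two sample paired t test design with an effect size of 1.25" and 15 per intensity group, stated power 91%. Taken as an independent two-sample t test (two-sided 5% assumed), the noncentrality is 1.25 × √(15/2) = 3.42 on 28 df, which gives 0.910. The figure reproduces. It concerns FDG, so test version does not touch it.

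**2. Model for the cognitive change.** Let E be the true exercise effect, d the difficulty difference (version B minus version A), p the practice gain from first to second visit, and s = +1 if rest comes first, −1 if exercise comes first. Change is exercise minus rest.

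- Version locked to condition (A at rest, B after exercise): change = E + d + s·p. Balancing order removes p; d stays in full.
- Version tied to visit number (A first, B second): change = E + s·(d + p). Balancing order removes both.

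**3. Which contrasts are exposed if version is locked to condition.**

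- Mean rest-to-exercise change: E + d, so it is biased by d.
- Moderate versus higher intensity: (E_high + d) − (E_mod + d) = E_high − E_mod. A constant d cancels, and it cancels from the diagnosis-by-intensity interaction for the same reason. In simulation with d = 0.3 and 15 per group, the bias was 0.00 and the type I error about 0.05.
- Change in cognition against change in lactate AUC: adding a constant to one variable alters neither slope nor correlation.
- ND versus AD comparison of the change: (E_AD − E_ND) + (d_AD − d_ND). This is affected only if difficulty differs by diagnosis. With d = 0.3 in AD and 0.1 in ND (both assumed), the spurious difference is 0.2.

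**4. Size for the exposed contrast.** Assume E = 0, d in SD units of the paired difference, and a two-sided 5% paired t test. The rejection rate comes from the noncentral t with noncentrality d√n on n − 1 df. Sample sizes are from V.A: "30 subjects in each diagnosis group with 15 individuals assigned to moderate and higher intensity acute exercise", which gives 15 per cell, 30 per diagnosis and 60 in all.

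| n | d = 0.1 | d = 0.2 | d = 0.3 |
|---|---|---|---|
| 15 | 0.07 | 0.11 | 0.19 |
| 30 | 0.08 | 0.19 | 0.36 |
| 60 | 0.12 | 0.33 | 0.63 |

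For n = 30 and d = 0.3, the noncentrality is 0.3 × √30 = 1.64 against a critical value of 2.05. The rate rises with n because the bias is fixed while the standard error shrinks.

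If the offset is instead stated in SD of the score, divide it by √(2(1 − r)), where r is the rest-exercise correlation. At r = 0.5 nothing changes. At an assumed r = 0.7, an offset of 0.3 becomes 0.3/√0.6 = 0.39, and the rates are 0.54 (n = 30) and 0.84 (n = 60).

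**5. Comparison of assignment rules.** Simulation with d = 0.3, p = 0.2, E = 0 and order balanced, no order term fitted:

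| Rule | Bias | Rejection, n = 28 | Rejection, n = 60 |
|---|---|---|---|
| Locked to condition | 0.30 | 0.32 | 0.62 |
| Tied to visit number | 0.00 | 0.03 | 0.03 |
| Crossed with order | 0.00 | 0.04 | 0.04 |

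Rates below 0.05 under the last two rules reflect extra spread. With version tied to visit, s·(d + p) = ±0.5 raises the variance of the change from 1 to 1.25 unless order is modelled.

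**6. Residual imbalance.** Fifteen is odd, so the best split in a cell is 8/7 and the mean of s is ±1/15. With d = 0.3, the version part left over is 0.3/15 = 0.02 SD.

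**The case against.** A reader might infer that the protocol allocates versions by condition. It does not say so. The sentence requires only that a participant's two sessions use different forms. Giving A at the first PET visit and B at the second satisfies it, and so does varying the pairing across participants. Under either of those, recorded versions and balance or modelling would deal with the problem. The defect is a missing rule that permits the bad case, not a stated bad rule.

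A reader might also infer that Aim 2's cognitive results as a whole are at risk. That goes too far. The only cognitive hypothesis with a stated direction concerns the link with lactate, which a constant offset leaves alone, as it does the intensity contrast and the diagnosis-by-intensity interaction. Tests with no alternate version are untouched, and cognition is not the primary outcome. What remains exposed is the mean rest-to-exercise change, for which the plan states no direction and no power, and the ND-AD comparison of that change if difficulty depends on diagnosis.

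The size is assumed as well: nothing in the documents shows that the versions differ in difficulty. The remedy is not free of side effects either. Exact balance is impossible in cells of 15, and tying version to visit adds order-related spread to contrasts that a constant offset would leave clean.

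All of this stands. It narrows the point and shapes the fix. It does not remove the point, because full confounding is compatible with the plan as written and could not be undone later.

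**Conclusion.** The point holds as a gap in specification with a potentially serious consequence for one estimate. Version assignment is not stated, only visit order is counterbalanced, and no version or order term is planned. If a form were locked to each condition, the whole difference in difficulty would pass into the Aim 2 mean rest-to-exercise cognitive change, and a larger sample would not reduce it.

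The false-positive rates, about 0.08 to 0.36 at n = 30 and 0.12 to 0.63 at n = 60, rest on four assumptions: versions locked to condition, a version difference of 0.1 to 0.3 SD of the paired difference, no true exercise effect, and a two-sided 5% paired test. They illustrate what the wording allows and do not predict what will happen. The plan should be changed on this point, but the primary analysis is not in question.

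**What to change.** Replace the sentence in II.E with: version A is given at the first PET visit and version B at the second, whichever condition that is. In addition:

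- Balance visit order as nearly as possible within each diagnosis-by-intensity group (8/7 in cells of 15).
- Record the version used at each session.
- In V.A, include a centred visit-order term in the cognitive change-score models, coded −½ and +½ so that the intercept weights the two orders equally. It absorbs version and practice effects together, and so removes the effect of the 8/7 imbalance and the added spread.

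The cost is a few lines of text, one item on the visit checklist and one degree of freedom; no testing is added. The downside is that version and practice effects can no longer be told apart, which the trial's aims do not require. If the sites already assign versions this way, the change only writes down existing practice.
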